### 6.3.2. Ultrasound procedure

Eligible patients will receive:

- a structured point of care ultrasound examination immediately at admission in emergency (or at the point of visit in ANC or ward) by the medical officer using the hand held device and following a simple checklist (Table1).
- the ultrasound examination will be repeated by an expert operator using a standard ultrasound machine in the scanner room of PCMH.

### 6.3.3. Portable Ultrasound Device

The portable ultrasound device to be used in the study is a convex probe type which work with compatible smart devices run by Android OS. Its frequency range is 3.5 MHz and maximum depth is 30cm. The screen of the smart phone or tablet is the interface, designed to be easy to use, focusing on minimum functions such as freeze, zoom, simple obstetric measurements and gray-scale adjustment. Detailed information on the device are provided in Appendix 2.

## 6.4. Safety consideration and follow up

### 6.4.1. Withdrawal of individual subjects

Patients can leave the study at any time for any reason if they wish to do so without any consequences. The investigator can decide to withdraw a subject from the study

for urgent medical reasons, e.g. when it becomes impossible to perform the ultrasound examination or this is deemed to interfere with patient care.

The study participants have the right to contact the ethics and review committee if they raise any issue or concern with the study (Office of the Sierra Leone Ethics and Scientific Review Committee, Ministry of Health and Sanitation, Directorate of Policy, Planning & Information (DPPI) [name]).

## **6.5.SAEs**

Because all proceedings in the method of this study are based on common clinical practice and ultrasound is a non-invasive procedure that cannot injure patients, there are no serious adverse events (SAEs) expected.

## **7. DATA MANAGEMENT AND STATISTICAL ANALYSIS**

### **7.1.Data management**

All patients will be identified with a unique study identification code. A logbook with the matching between patient number and name will be stored digitally and in paper. The paper version will be stored behind a lock and the digital form will be protected with a password. The logbook will be the only document containing patient identifier information. Data will be stored an additional 15 years after the study's completion.

#### **7.1.1.Data capture**

Data is collected on paper checklists and case report forms (CRFs) and subsequently transcribed onto an Internet-based electronic CRF (<https://www.kobotoolbox.org>). Access to the data-entry system is protected by a personalized username and password. Patients are identified with a study identification code, hence there will be no patient identifier data transcribed on the online CRF.

#### **7.1.2.Data sharing**

Data derived from this study will be shared with the clinical team directly responsible for patient's care and with hospital leadership and management team for monitoring and/or audit purposes. **Specifically, a copy of the final expert report performed with the conventional apparatus will be attached to the patient's clinical chart to be visualized by the clinical team responsible for patient's care.** After publication of the primary results, on request the pooled dataset will be available for secondary analysis, after judgment and approval of scientific quality and validity of the proposed analysis by the steering committee.

#### **7.1.3.Data handling and record keeping**

The anonymized data will be stored in a secure database to guarantee the privacy of study subjects. Only local investigators will have access to the database and matching log-book.

## **7.2. Statistical analysis**

Data will be reported as mean and standard deviation or median with interquartile range (continuous data), and as frequency and percentage (categorical data). The agreement between the hand-held device and the conventional apparatus on categorical findings scoring will be assessed using diagnostic accuracy and Cohen's K statistics. When appropriate, comparison between subgroups will be performed using Student's t test, ANOVA, Mann-Whitney test or Kruskal-Wallis test for continuous data, and with Chi-square test or Fisher's test for categorical data. A p-value less than 0.05 will be considered statistically significant. Statistical analyses will be performed using R (R Foundation for Statistical Computing, Vienna, Austria). The sensitivity, specificity, positive predictive value, and negative predictive value for each dichotomous ultrasound finding acquired with hand held devices against the reference diagnoses with conventional apparatus will be assessed when appropriate. Quality of images will be assessed by standardized scoring system from 0 to 4 (0= no meaningful images; 1 = poor, not sufficient for interpretation; 2 = good, acceptable for interpretation; 3= excellent, minor suggestions for interpretations; 4 = outstanding, no suggestions for interpretations). All analyses will be conducted after the end of patient recruitment and no interim analyses are planned.

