## 1. PROJECT SUMMARY

**Rationale:** The majority of obstetric emergencies are identified through clinical examination, which cannot be substituted by ultrasound. However, just as a laboratory exam, ultrasonography can provide swift point of care information on fetus presentation, viability, placenta position, quantity of amniotic fluid and presence of abdominal fluid to inform the clinical reasoning and therapeutic escalation. Ultrasound literature in low-resource settings has favoured antenatal care (ANC) rather than the emergency setting. Also, hand-held ultrasound machines may not be as performant as traditional machines used by expert operators but to date is still to be tested in a low resource setting.

**Objective:** to assess the *reliability* of **ultrasound findings** measured by hand held ultrasound probes used by operators with variable experience in a low resource hospital.

**Hypothesis:** There is substantial agreement between simple ultrasound findings identified using hand held ultrasound devices and the reference standard.

**Study design:** a prospective observational diagnostic accuracy study.

**Study population:** parturients admitted to the Princess Christian Maternity Hospital (PCMH) in Freetown, Sierra Leone.

**Sample size:** no formal sample size calculation is performed. Based on current rates of admissions to the PCMH we expect to perform obstetrical ultrasound scan in at least 300 patients during a 2–months study period.

**Methods:** 4 trained physicians (3 naive and 1 intermediate ultrasound users) will perform the ultrasound investigations using the hand held device and complete a structured predefined report form of obstetric ultrasound findings at patient admission or according to clinical indications after admission. These will be compared with the reference standard, i.e. an ultrasound examination performed by a specialist gynecologist/obstetrician using a conventional apparatus in the hospital ultrasound room.

**Main study parameters/primary endpoints:** The mean diagnostic accuracy among nine ultrasound obstetric findings collected with hand held devices versus the reference standard.

**Nature and extent of the burden and risks associated with participation, benefit and group relatedness:** Ultrasound is a non–invasive and painless procedure without additional risks.

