#### **4.1.4.Secondary hypothesis**

1. The diagnostic accuracy will be significantly higher for specific 'easier to detect' *individual ultrasound findings* such as intrauterine pregnancy, amniotic fluid estimation, cephalic presentation, and presence of abdominal fluid.
2. The diagnostic performance of the ultrasound *naïve operator* is significantly different from the intermediate operator only for more complex ultrasound findings such as fetal heart, presence of retroplacental hematoma, placenta location, estimation of gestational age and detection of multiple pregnancy.
3. The proportion of complete examinations is >90% and quality of images as estimated by a simple visual scoring system is high (more or equal to 3).

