## **5.2. Sample size calculation**

Sufficient information to perform a formal sample size calculation is lacking. During a 2-month period all patients meeting the inclusion and exclusion criteria will be recruited. Based on current rates of admissions in the mentioned services, we expect to recruit at least 300 patients (75 patients per operator, 15 for each of the 5 inclusion categories) during a 2 months data collection period.

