### **6.3. Study procedures**

#### **6.3.1. Training of operators**

The ultrasound operators will receive a 2-week training course. The 1st week training consists of lectures on basic science of ultrasound and tomography, demonstrations by an expert obstetrics sonographer, and hands-on practice at the scanning room of PCMH. The second week of training will focus on how to operate the hand-held ultrasound device, training on the standard operating procedure (SOP) and case report form (CRF) completion.

**Table 2. Ultrasound findings.** Abbreviations: GA, gestational age; FH, fetal heart; MVP, maximum vertical pocket, APH, antepartum hemorrhage; ANC, antenatal clinic.

	Inclusion category	Finding 1	Finding 2	Finding 3	Finding 4
1	Vaginal bleeding in early pregnancy	Intra-uterine pregnancy: yes/no	FH: yes/no	Free fluid in abdomen: yes/no	None
2	Pre-eclampsia	FH: yes/no	Amniotic fluid MVP<2cm: yes/no	GA: ≤34 or >35 weeks	Cephalic presentation: yes/no
3	APH in third trimester	Placenta low lying: yes/no	FH: yes/no	Retroplacental hematoma: yes/no	Amniotic Fluid MVP<2cm: yes/no
4	Prolonged/ obstructed labor	FH: yes/no	Multiple pregnancy: yes/no	Cephalic presentation: yes/no	Amniotic Fluid MVP<2cm: yes/no
5	ANC High Risk Pregnancy*	Cephalic presentation: yes/no	Multiple pregnancy: yes/no	FH: yes/no	Amniotic Fluid MVP<2cm: yes/no
				Placenta low lying: yes/no	GA: ≤34 or >35 weeks

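### Section 7.2 names only independent-sample tests, but hypothesis 1 compares findings measured largely in the same women, so a method clustered on patient is needed

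*Protocol*

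**What the plan says.** Section 7.2 sets out the inferential methods. Where suitable, "comparison between subgroups will be performed using Student's t test, ANOVA, Mann-Whitney test or Kruskal-Wallis test for continuous data". Yes/no outcomes are to be compared between groups "with Chi-square test or Fisher's test for categorical data". The threshold follows: "A p-value less than 0.05 will be considered statistically significant". No paired or clustered method is named.

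The data these tests would meet are described elsewhere in the protocol:

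- **Primary endpoint (section 1):** "The mean diagnostic accuracy among nine ultrasound obstetric findings collected with hand held devices versus the reference standard". Section 6.1.1 describes it as a mean aggregated accuracy. No test or interval is stated for it.
- **Secondary hypothesis 1 (section 4.1.4):** "The diagnostic accuracy will be significantly higher for specific 'easier to detect" findings, listed as intrauterine pregnancy, amniotic fluid, cephalic presentation and abdominal fluid.
- **Secondary hypothesis 2 (section 4.1.4):** naive and intermediate operators differ only for the more complex findings, listed as fetal heart, retroplacental hematoma, placenta location, gestational age and multiple pregnancy.
- **Table 2 (section 6.3.1):** three findings for early-pregnancy bleeding (the third is "Free fluid in abdomen: yes/no"), four each for pre-eclampsia, antepartum hemorrhage and prolonged or obstructed labor, and six for high-risk antenatal patients.
- **Numbers:** at least 300 patients, "75 patients per operator, 15 for each of the 5 inclusion categories" (section 5.2), scanned by "4 trained physicians (3 naive and 1 intermediate ultrasound users" (section 1).

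**The concern.** Hypothesis 1 claims a significant difference between types of finding. Fetal heart (on the complex list) is assessed in all five categories, and amniotic fluid (on the easy list) in four of them. The two sides of the comparison therefore come largely from the same women, scanned by the same operator in the same session. If a scan that is difficult for one finding tends to be difficult for the next, the observations are correlated, and no test on the list allows for that.

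The direction of the error depends on the comparison:

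- **Across findings, within women:** positive correlation shrinks the variance of the difference. An independent-sample test overstates that variance and loses power.
- **Between operator groups, on findings pooled over types:** each woman contributes several correlated observations to one side only. An independent-sample test understates the variance and rejects too often.
- **An interval for the composite:** treating the findings as independent makes it too narrow.

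The point estimates (composite, per-finding accuracy, sensitivity, specificity, kappa) are not affected. What is at stake is the calibration of p-values and of any interval.

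**Working it through.** **Inputs.** Section 5.2: 4 operators × 5 categories × 15 = 300 women, which reproduces the stated figure, so 60 per category. Section 1: 3 × 75 = 225 women with naive operators and 75 with the intermediate operator. Table 2: m = 3, 4, 4, 4, 6 findings per woman, so 60 × 21 = 1,260 findings (mean 4.2).

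**Assumptions.** One category per woman. (Section 5.1.1 allows more than one, which would raise m for some.) Equal accuracy for all findings under the null, two-sided alpha 0.05, and a common within-patient correlation ρ. The protocol gives no ρ; 0.1 to 0.3 is shown, and ρ = 0 means no error.

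**1. Hypothesis 1: easy versus complex findings, pooled.** With the lists in section 4.1.4, the five categories have a = 2, 2, 1, 2, 2 easy findings and b = 1, 2, 3, 2, 4 complex ones. The totals are E = 60 × 9 = 540 and C = 60 × 12 = 720.

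True variance over independence variance = 1 + ρ × [Σa(a−1)/9² + Σb(b−1)/12² − 2Σab/(9×12)] / (1/9 + 1/12)
= 1 + ρ × [8/81 + 22/144 − 42/108] / 0.1944
= 1 − 0.706ρ.

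True alpha = 2[1 − Φ(1.96/√ratio)].

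**2. One pair of findings: fetal heart (300 women) versus amniotic fluid (240 of the same women).** Ratio = 1 − ρ × (2/300)/(1/300 + 1/240) = 1 − 0.889ρ.

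**3. Naive versus intermediate, pooled over findings (945 versus 315).** Design effect = 1 + (Σm²/Σm − 1)ρ = 1 + (93/21 − 1)ρ = 1 + 3.43ρ. The same design effect applies to an interval for the pooled proportion of correct findings.

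**4. Unweighted mean of nine accuracies.** In units of 60 women, the findings are assessed in: intrauterine pregnancy 1, abdominal fluid 1, hematoma 1, gestational age 2, placenta 2, multiple pregnancy 2, cephalic 3, amniotic fluid 4, fetal heart 5. The independence variance is proportional to Σ1/n = 3 + 1.5 + 0.333 + 0.25 + 0.2 = 5.283. The covariance terms, summing 1/(n_f n_g) over ordered pairs of different findings f and g within each category, are 2.8 + 1.183 + 2.45 + 1.183 + 4.25 = 11.867. Design effect = 1 + (11.867/5.283)ρ = 1 + 2.25ρ.

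| Quantity | ρ = 0.1 | ρ = 0.2 | ρ = 0.3 |
|---|---|---|---|
| Easy vs complex: variance ratio | 0.929 | 0.859 | 0.788 |
| Easy vs complex: true alpha | 0.042 | 0.034 | 0.027 |
| Fetal heart vs amniotic fluid: true alpha | 0.040 | 0.031 | 0.022 |
| Pooled operator comparison: design effect | 1.34 | 1.69 | 2.03 |
| Pooled operator comparison: true alpha | 0.091 | 0.131 | 0.169 |
| Correct/naive interval width, pooled proportion | 1.16 | 1.30 | 1.42 |
| Correct/naive interval width, mean of nine | 1.11 | 1.20 | 1.29 |

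**5. Check by simulation.** With 20,000 beta-binomial replicates at accuracy 0.8 and 0.9 and ρ from 0.1 to 0.3, the pooled operator comparison rejected in 9.0% to 16.7% at the ends of the range, and easy versus complex in 4.4% to 2.7%. Fetal heart alone, 225 versus 75 women, stayed at 4.7% to 5.2% for every ρ from 0 to 0.3. One finding gives one value per woman, so that comparison is sound.

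**The case against.** The strongest reply is that section 7.2 ties no test to hypothesis 1. It speaks of subgroups and says the tests apply where suitable. Subgroups most naturally means groups of patients or operators, where these tests are valid with one value per woman. How hypothesis 1 is tested could then be a detail left to a statistical analysis plan that is not at hand. This stands in part: the protocol does not prescribe chi-square across findings. But it does state a hypothesis of significant difference across findings and does list its tests, and none of those listed suits that hypothesis.

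A reader might infer three stronger things, which the protocol does not support:

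- **That the operator comparison is invalid, with up to 17% false positives.** That figure belongs only to a comparison pooled over findings, which the protocol does not explicitly prescribe. Hypothesis 2 concerns specific findings, and section 5.2 assigns each woman to one operator. Chi-square or Fisher is then valid finding by finding. Even for a composite, a t or rank test on one score per woman would avoid the clustering, though no such score is specified. Only if the inter-observer endpoint in section 6.1.2 meant that both operator groups scan the same women would single-finding comparisons also be paired; section 5.2 suggests they do not.
- **That the planned intervals are wrong.** The protocol states no interval or error bar for any pooled or cross-finding quantity. One can say only that an interval computed as if findings were independent would be too narrow.
- **That hypothesis 1 risks false claims.** With positive within-patient correlation the error there is conservative.

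It is also fair that the section 1 wording fits an unweighted mean of nine accuracies better than a pooled proportion. The factors 1.11 to 1.29 are then the relevant ones.

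**Conclusion.** The point holds in limited form. The tests named in section 7.2 do not fit hypothesis 1, which compares findings measured largely in the same women. Used there, chi-square or Fisher would have a true alpha of about 0.042 to 0.027 instead of 0.05, a loss of power on a secondary hypothesis. Two further consequences are conditional: a true alpha of about 0.09 to 0.17 if operator groups are compared on pooled findings, and a composite interval too narrow by a factor of 1.11 to 1.29 (mean of nine) or 1.16 to 1.42 (pooled proportion) if findings are treated as independent. Single-finding operator comparisons are valid as planned.

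All these sizes rest on an assumed, exchangeable within-patient correlation of 0.1 to 0.3. At zero there is no error, but zero is hard to defend when one operator scans one woman in one session. The change is worth making because it is cheap and the hypothesis is stated in terms of significance.

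**What to change.** In section 7.2:

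- Test hypothesis 1, and any operator comparison pooled over findings, with a method clustered on patient. Examples are a logistic GEE with patient as cluster or a patient-level bootstrap of the difference. Keep the model to few terms: with 15 women per operator and category and perhaps few errors, a model with full finding, category and operator terms may meet empty cells.
- Give the composite a confidence interval from a bootstrap that resamples patients, and say whether the composite is the unweighted mean of nine accuracies or the pooled proportion.
- Keep chi-square or Fisher for one finding at a time between different patients.

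The cost is a few lines of text, slightly more analysis work with standard R tools, and somewhat wider composite intervals. No new data and no change to enrolment are needed.

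Clustering on patient does not separate operator from experience level. With one intermediate operator the two are confounded, and the report should say so.

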#### **6.1.2. Secondary study parameters/endpoints**

1. Detailed diagnostic accuracy for each of the nine ultrasound findings.
2. Inter-observer agreement on ultrasound findings between naïve and intermediate operators.
3. Mean 'quality of image score' (0-4) for each of the nine ultrasound findings.
4. Proportion of complete ultrasound examinations i.e. with all pre specified findings allocated for the category being completed.

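### Secondary hypothesis 2 would be judged by sorting nine findings into p<0.05 or not, which misleads in both directions; one experience-by-complexity contrast tests it better

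*Protocol*

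**What the plan says.** Protocol section 4.1.4 words two secondary hypotheses in terms of significance. The first reads "The diagnostic accuracy will be significantly higher for specific 'easier to detect" and goes on to name four findings: intrauterine pregnancy, amniotic fluid, cephalic presentation and abdominal fluid. The second states that the naive operator's performance "is significantly different from the intermediate operator only for more complex ultrasound findings such as fetal heart, presence of retroplacental hematoma", and the list continues with placenta location, gestational age and multiple pregnancy. Four plus five accounts for all nine findings in Table 2.

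Section 6.1.2 lists as a secondary endpoint "Detailed diagnostic accuracy for each of the nine ultrasound findings". Section 7.2 provides for subgroup comparisons, where appropriate, "with Chi-square test or Fisher's test for categorical data", and sets a single threshold: "A p-value less than 0.05 will be considered statistically significant".

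The layout comes from two places. The project summary says "4 trained physicians (3 naive and 1 intermediate ultrasound users) will perform the ultrasound investigations". Section 5.2 says "we expect to recruit at least 300 patients (75 patients per operator, 15 for each of the 5 inclusion categories".

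**The concern.** Hypothesis 2 is a statement about a pattern: a difference on the complex findings and none on the others. The protocol's tools for judging it are separate tests at 0.05, so the natural reading is to run nine naive-versus-intermediate tests and see which side of 0.05 each falls.

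That procedure is weak in both directions. Chance alone can produce a significant difference somewhere, and five of the nine places it can fall are findings for which the hypothesis predicts one. In the other direction, a non-significant result on an easier finding would count in favour of the hypothesis even where the comparison is too small to detect a large gap. What is at stake is secondary objective 2, whether reliability depends on operator experience, and any conclusion about which findings need the more experienced operator.

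**Working it through.** **Inputs from the protocol.** Threshold 0.05 per test (7.2). Nine findings (6.1.2). Three naive operators and one intermediate (project summary). 75 patients per operator, 15 per category (5.2). Check on the total: 4 operators x 5 categories x 15 = 300 = 4 x 75, which reproduces the stated 300. Each category therefore gives 3 x 15 = 45 naive and 15 intermediate examinations.

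**Categories per finding (c), from Table 2.** Fetal heart 5; amniotic fluid 4; cephalic presentation 3; gestational age, low-lying placenta and multiple pregnancy 2 each; intrauterine pregnancy, free fluid and retroplacental hematoma 1 each. A finding recorded in c categories is compared on 45c versus 15c patients.

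**Assumptions.** The protocol gives no expected accuracy. I take a common true accuracy of 0.80 to 0.98 for the false-positive calculation, and 0.95 (intermediate) versus 0.80 (naive) for power. Tests are two-sided.

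**Step 1, nominal benchmark.** With k independent tests of size 0.05, P(at least one false positive) = 1 - 0.95^k.
- Nine findings: 1 - 0.95^9 = 0.370.
- Five complex findings: 1 - 0.95^5 = 0.226.

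Findings share patients, so independence is only a benchmark. For nine tests of exact size 0.05, simulation gives 0.27 at correlation 0.5 and 0.17 at 0.8.

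**Step 2, exact sizes on the planned layout.** For each finding, the size of Fisher's test is the sum, over all pairs of binomial counts with common accuracy p, of their probability where the Fisher p-value is below 0.05. The nine sizes are combined as 1 - product(1 - size). Worked at p = 0.90, the sizes are 0.0210 (c=1, three findings), 0.0304 (c=2, three findings), 0.0367 (c=3), 0.0391 (c=4) and 0.0382 (c=5). So 1 - 0.9790^3 x 0.9696^3 x 0.9633 x 0.9609 x 0.9618 = 0.238.

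| Assumed common accuracy | Nine Fisher tests | Five complex only | Nine uncorrected chi-square tests | Nine continuity-corrected chi-square tests |
|---|---|---|---|---|
| 0.80 | 27% | 17% | 38% | 20% |
| 0.90 | 24% | 14% | 33% | 16% |
| 0.95 | 19% | 11% | 29% | 10% |
| 0.98 | 10% | 6% | 21% | 4% |

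Dependence within patients changes this only modestly. In a simulation on this layout, using Fisher when an expected count was below 5 and chi-square otherwise, a latent within-patient correlation of 0.5 moved the nine-test figure at accuracy 0.90 from 0.267 to 0.234.

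**Step 3, what non-significance shows.** This is the same sum as in step 2, with accuracies 0.95 (15c patients) and 0.80 (45c patients):

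| c | Naive vs intermediate patients | Fisher power | Findings |
|---|---|---|---|
| 1 | 45 vs 15 | 9% | intrauterine pregnancy, free fluid (easier); hematoma (complex) |
| 2 | 90 vs 30 | 48% | gestational age, placenta, multiple pregnancy (complex) |
| 3 | 135 vs 45 | 71% | cephalic presentation (easier) |
| 4 | 180 vs 60 | 85% | amniotic fluid (easier) |
| 5 | 225 vs 75 | 92% | fetal heart (complex) |

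For one and the same true gap, whether a finding reaches 0.05 depends mainly on how many categories record it, not on how complex it is.

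**The case against.** The strongest reply is that multiplicity among secondary tests is commonly settled in a statistical analysis plan, which is not at hand, and that section 7.2 never claims a 5% family-wise rate. This stands as far as it goes: the mere lack of an adjustment is not the point. But the wording of hypothesis 2 and the flat threshold are in the protocol, and an adjustment would not repair an inference that treats non-significance as evidence of no difference.

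Second, no passage explicitly plans nine tests. The operator endpoint in 6.1.2 is inter-observer agreement, both lists in 4.1.4 are introduced as examples, and subgroup tests are to be used when appropriate. That is fair, and the figures are therefore conditional on nine tests being run. It remains true that the two lists together exhaust the nine findings and that the hypothesis contrasts one list with the other.

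Third, at least one false positive may not be the relevant error. If hypothesis 2 requires all five complex findings to be significant, its false-positive rate cannot exceed 0.05 without any adjustment. That is correct. But under the assumed 0.95 versus 0.80 gap, this reading could succeed at most about 9% of the time, because hematoma alone has that power. The text does not say which reading applies.

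Three stronger readings might be inferred and are not supported.
- A false difference is not more likely than not: every nine-test figure above is below one half, and with continuity-corrected chi-square at accuracy 0.98 it is below 5%.
- Hypothesis 1 cannot be assigned a number of further tests, because its comparator is not stated.
- The primary conclusion is not at risk, because the primary endpoint in 6.1.1 is one aggregated accuracy measure.

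**Conclusion.** The point holds for hypothesis 2. Sorting nine findings by p<0.05 is an unsound test of a claim that operators differ on complex findings only. If nine tests are run with no true difference, the chance of at least one false difference is up to 37% nominally and about 10% to 27% with Fisher tests on the planned layout. Non-significance on a one-category finding carries little information, at about 9% power.

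These sizes rest on the expected 300 patients being spread evenly over operators and categories, on assumed accuracies of 0.80 to 0.98 (0.95 versus 0.80 for power), and, for the 10% to 27%, on combining findings as if independent. The consequence is confined to the secondary conclusions on operator experience. It is worth correcting before analysis and does not threaten the study as a whole.

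**What to change.** In 4.1.4, reword hypothesis 2 so that it no longer says operators are significantly different only for certain findings. State instead that the gap between naive and intermediate operators is larger on the complex findings than on the easier ones, and close both lists so that each of the nine findings belongs to one group.

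In 7.2:
- Test hypothesis 2 with one experience-by-complexity contrast: the naive-minus-intermediate accuracy gap on the five complex findings, minus the same gap on the four easier findings, allowing for findings shared within patients.
- Test hypothesis 1 with one contrast of easier against complex findings, again allowing for shared patients.
- Do not make either test conditional on the other; they serve separate secondary objectives.
- Report the nine per-finding operator comparisons as exploratory estimates with 95% confidence intervals. If significance is to be claimed for single findings, use Holm-adjusted p-values across the nine (smallest threshold 0.05/9 = 0.0056).

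The cost is wording in two sections and two contrasts, with no new data. Single-finding claims lose some power under Holm or become exploratory. With only one intermediate operator, the contrast still cannot separate experience from that individual, and the report should say so.
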